5.2.6 Proton Beam Physical Factors

Proton treatments will be delivered at the Francis H. Burr Proton Therapy Center at the Massachusetts General Hospital using a 240 MeV cyclotron. At MDACC, proton treatments will be delivered at the MDACC Proton Therapy Center using a 250 MeV synchrotron. Treatments will usually be administered as one daily fraction, 5 days per week.

5.2.6 Proton Beam Modification/Blocking

Beam shaping will be accomplished using primary collimation by the gantry jaws. The penumbra is large and field shaping by secondary collimation will be necessary using a downstream custom cut brass aperture. Apertures will be constructed on brass alloy of sufficient thickness to attenuate 99.9% of protons. Apertures will be cut to be parallel to beam divergence. 3-D lucite compensators may be fabricated to conform dose to the target at the distal aspect.

5.2.8 Quality Assurance and Rapid Review of Treatment Plans

To ensure protocol compliance, the treatment plans for the first three patients treated at each site will be reviewed by the Principal Investigator and Participating Site's PI. As described in Section 12.1.3, below, plans will be submitted to the Advance Technology QA Center at Washington University, St Louis (ATC) for this protocol. The plans will be sent to the ATC upon approval by the treating physician, and the PI and/or Participating Site PI will review and confirm protocol compliance within three working days of the start of treatment.

5.2.9 Beam Verification:

Digitally reconstructed radiography (DRR) will be done for treatment planning and verification and will be performed daily during treatment.

5.2.10 Dose Uniformity

Dose gradient in CTV should remain within +7% to -5% of prescribed dose.

5.2.11 Dose Derification

A physicist co-investigator at each participating institution will be responsible for dose verification.

5.2.12 Concurrent Protocol

For patients who are enrolled on co-existing protocols such as COG, physicians will adhere to the radiation therapy guidelines of the companion protocol which specify their own guidelines for the following parameters: total dose, dose per fraction, fractionation schedule and sequencing with other therapy (e.g. chemotherapy). If any questions or discrepancies arise, then contact [name], MD at [contact] ([contact]) before beginning radiation treatments.

5.2.13 Treatment Delay

To avoid treatment delays resulting from the machine being down, photon or electron (if appropriate) beam radiation can be administered. The maximum dose for both the posterior fossa and spine will be 20% of the prescribed dose (e.g. 20% of the spine at 36 Gy would be a maximum of 4 spine treatments or 7.2 Gy). Delay in the start of CSI proton therapy shall not exceed 2 weeks in M0 patients and 1 week in M+ patients.

5.2.14 Emergent Radiation Therapy

For patients who require emergent RT when a proton slot is not available, photon (or electron beam) therapy may be delivered at the maximum dose for the posterior fossa and at 20% of the maximum dose for the spine (e.g. 20% of the spine at 36 Gy would be a maximum of 7.2 Gy).

5.3 General Concomitant Medication and Supportive Care Guidelines

There are no required concomitant medications in this study. No other radiotherapy besides that which was outlined above may be used during study treatment. Patients may receive all concomitant therapy deemed necessary to provide optimal support.

5.4 Duration of Therapy

Duration of therapy will depend on individual response, evidence of disease progression and tolerance. In the absence of treatment delays due to adverse events, treatment will continue until the prescribed dose of radiation therapy is delivered or until one of the following criteria applies:

- Disease progression,
- Intercurrent illness that prevents further administration of treatment,
- Unacceptable adverse event(s),
- Participant decides to withdraw from the study, or
- General or specific changes in the participant's condition render the participant unacceptable for further treatment in the opinion of the treating investigator.

5.5 Criteria for Removal from Study

Participants will be removed from treatment or active follow up when any of the criteria listed in Section 5.4 applies. Participants removed from treatment or active follow up for disease progression will continue to be followed for survival status only. The reason for removal and the date the participant was removed must be documented in the study-specific case report form (CRF). Alternative care options will be discussed with the participant.

5.6 Duration of Follow Up

Participants will be followed for at least 8 years after completion of radiation therapy or until death, whichever occurs first. Participants will be invited to return to the treating institution for annual follow up visits. Participants who do not live in the local area of their treating institution will be allowed to obtain follow up care at home and forward records to the study team at the treating institution. Once participants have reached 5 years post treatment, they may be compensated for a one time return visit to MGH if grant funding is available.

In the event of unusual or life-threatening complications, participating investigators must immediately notify the Principal Investigator [name] via the Coordinating Center at [contact].

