1.2 Primary Objectives

Analysis of primary objectives outcomes will be done separately for high risk and standard risk groups.

- 1.2.1 To estimate the incidence and severity of ototoxicity (especially in combination with cisplatin-based chemotherapy) at three (3) and five (5) years following the completion of radiation therapy.
- 1.2.2 To describe the incidence of endocrine dysfunction (neuroendocrine and end organ defects).
- 1.2.3 To describe the incidence and severity of neurocognitive sequelae overall and in subgroups based on whether or not methotrexate was used as part of the treatment regimen.

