7. DRUG FORMULATION AND ADMINISTRATION: N/A

8. CORRELATIVE/SPECIAL STUDIES: N/A

9. STUDY CALENDAR

Baseline evaluations are to be conducted within 35 days prior to start of protocol therapy. Scans must be performed within 6 weeks prior to the start of therapy. CSF sampling can be completed any time prior to start of protocol therapy.

Table 2: Required Data

Tests and Observations	Pre-Study/ Baseline	During Radiation	Follow Up (1)
Informed Consent and registration	X		
Biopsy or attempted resection	X		
Pathology Review	X		
Medical History	X		X (2)
Physical Exam	X	X (2)	X (2)
Endocrine Evaluation	X (3)		X (3)
CSF sampling if M0 disease	X (4)		
CBC	X (5)		X (5)
Serum Chemistries	X (6)		X (6)
MRI or CT of the brain	X (7)		X (7)
MRI of the entire spine	X (8)		X (8)
Audiogram	X (9)	X (9)	X (9)
Neurocognitive Testing	X (10)		X (10)

Notes:

(1) Follow up, except for neurocognitive testing, is to be completed annually (+ or – 6 months) from the completion of study treatment. Follow up is highly recommended, but not required.

(2) Medical history and physical exams during radiation treatment is to be completed weekly and may include only the acute toxicity assessment and other pertinent objective findings. Medical history and physical exams at follow up are recommended, but not required.

(3) Baseline endocrine evaluation to be completed no later than 2 months after the start of radiation. Evaluation includes Tanner stage assessment by physical exam, bone age (plain film of the wrist), and body proportion measurements. Bone age, Tanner Stage assessment, and body proportion measurements collected will be at the discretion of the study endocrinologist. Recommended measurements include sitting height (sitting height preferred, but pubic symphysis to floor acceptable), standing height, leg span, and arm span. Recommended labs for endocrine evaluation are TSH, Free T4, Cortisol, IGF-1, IGF-BP3, LH, FSH, estradiol (females) and testosterone (males) – am levels preferred,

(4) CSF sampling can be done any time prior to the start of protocol therapy. CSF sampling must be completed no later than ten days after the start of radiation. If sampling performed less than 10 days after surgery is positive, it should be repeated.

(5) CBC required labs are ANC, Platelets, Hematocrit. CBC with diff. is required at baseline. Annual follow up CBC's are suggested, but not required

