(6) Chemistries required at baseline and that are suggested, but not required, for follow up are: albumin, alk phos, T bili, BUN, calcium, chloride, glucose, potassium, total protein, sodium, AST, ALT, Pregnancy test (if applicable and at pre-study only).

(7) Pre-Study brain MRI or CT includes pre-op and post-op imaging, post-op to be done within 21 days of surgery (preferably within 72 hours of surgery; intra-operative MRI as allowed). Brain MRI or CT at follow up is recommended, but not required.

(8) Pre-study spine MRI should be from the time of diagnosis (preferably pre-op). Spine MRI at follow up is recommended, but not required.

(9) Baseline audiogram must be completed within 2 months after the start of radiation. Audiograms are recommended, but not required, for patients receiving platinum based chemotherapy prior to the beginning of each cycle. Follow up audiograms are recommended annually. Additional audiograms, if done, will be collected and included in the data set.

(10) Baseline neurocognitive testing must be completed no later than 9 months after the start of radiation. Follow up testing is recommended starting one year after the previous exam, at one, three, and five years post-radiation (+ or – 12 months).

Patient Assessments:

The required tests and evaluations prior to, during and following CSI are shown in table 2. Patients will require acute side effect assessment during radiation therapy as detailed in section 9.1 below. Acute side effects from RT are defined as those effects that are attributable to the effects of radiation and occur from commencement of RT to 90 days following completion of RT.

Patients will be assessed for late side effects or complications which are defined as those effects that are attributable to the effects of radiation and occur > 90 days following completion of RT.

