9.2.2 Audiology evaluation

Audiograms are required and should be done prior to start of radiation. Audiograms should be obtained on a yearly basis as well (see table 2). Additionally regular audiograms are recommended but not required to be performed at the patient's home institution prior to each cycle of platinum based chemotherapy in accordance with the standard of care because platinum chemotherapy can cause acute hearing loss. If the baseline audiogram cannot be completed prior to the start of radiation, it must be completed within 2 months of the beginning of radiation therapy. Each ear (left and right) should be tested and recorded separately.

Grading of sensorineural hearing loss will be according to the CTEP Active Version of CTCAE.

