14.1 Study Design/Endpoints

Accrual goals are 60 standard-risk and 30 high-risk patients. In the pediatric MB population treated with conventional photon CSI, 3-year progression-free survival of standard-risk patients is in the 75-80% range depending on the concurrent use of chemotherapy, while 65-70% is reported among high-risk patients. Thus, 48 standard-risk and 20 high-risk patients are projected to be evaluable for late complications at 3 years following the CSI completion; patients who progress or die sooner will not contribute in the analysis of late complications.

The primary endpoint of ototoxicity at 3 years following completion of radiation therapy will be based on failure events defined by grade 3 or 4 sensorineural hearing loss (SNHL) according to COG criteria. They include progressive hearing decrease to grade 3 or 4 following mild or moderate loss (grade 1 or 2) typically experienced during platinum-based chemotherapy. All patients who have audiology assessments prior to censorship will contribute to the actuarial analysis. Patients will be censored in the event of death, drop out or progression of disease. The historical rates of late SNHL is in the 50% range among pediatric MB patients [9, 10] treated with conventional CSI and cisplatin-based chemotherapy. We shall conclude proton therapy leads to an improvement in the high-risk group if 7 or fewer of 20 patients were to experience grade 3 or 4 SNHL at 3 years following completion of radiation therapy. The decision rule is associated with 77% power if the SNHL rate were truly reduced to 30% among the high-risk patients. In contrast, the probability is only 13% for concluding incorrectly an improvement if the underlying SNHL rate were 50%. In the null hypothesis for the standard-risk group, we assume conventional CSI and cisplatin-based chemotherapy is associated with an SNHL rate less than 50% due to their lower CSI dose, in particular, 40%. We shall conclude proton therapy leads to an improvement in the standard-risk group if 14 or fewer of 48 patients were to experience grade 3 or 4 SNHL at 3 years following completion of radiation therapy. The decision rule is associated with 80% power if the SNHL rate were truly reduced to 25% among the standard-risk patients. In contrast, the probability is only 8% for concluding incorrectly an improvement if the underlying SNHL rate were 40%.

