14.4 Analysis of Endpoints

Progression-free survival is measured from the start of radiation therapy to the date of documented disease progression or death in the absence of progression. Patients who have not progressed or died will be censored at the time of last follow up. Progression-free survival will be estimated by the Kaplan-Meier method. Acute effects will be summarized according to specific events with exact 95% confidence intervals for binary data. The incidence of late complications will be based on actuarial estimates, primarily at 3 years. Patients who die, progress, or are lost to follow up prior to 3 years will be censored. Other factors which may influence late complications will be explored in multivariate models, including gender, age, radiation dose to the posterior fossa, dose volume histogram of the normal tissue as well as drugs, dosages and sequencing of the chemotherapy regimen. In addition, we shall control for pre-existing hearing deficits in the analysis of ototoxicity, while methotrexate usage will be of interest in the analysis of neurocognitive functioning among high-risk patients. Multivariate analyses will be primarily exploratory due to the modest patient numbers in each risk group.

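### With optional audiograms, a right-censored 3-year actuarial estimate can understate hearing loss and favour a false claim of improvement; use an interval-censored estimate

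*Combined protocol and SAP*

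**What the plan says.** All references are to the Combined protocol and SAP.

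- **Time points.** Objective 1.2.1 asks for the incidence and severity of ototoxicity "at three (3) and five (5) years following the completion of radiation therapy".
- **Estimator.** Section 14.4: "The incidence of late complications will be based on actuarial estimates, primarily at 3 years". Patients who die, progress or are lost before 3 years are censored.
- **Who counts.** Section 14.1: "All patients who have audiology assessments prior to censorship will contribute to the actuarial analysis". Censoring is for death, drop-out or progression.
- **Decision.** Section 14.1 declares an improvement if grade 3 or 4 sensorineural hearing loss (SNHL) at 3 years occurs in at most 14 of 48 standard-risk or 7 of 20 high-risk patients.
- **Testing.** Section 9, note 1: "Follow up is highly recommended, but not required". Note 9: "Follow up audiograms are recommended annually". Section 9.2.2 says audiograms should be yearly but does not make follow-up tests mandatory. Section 9.2.1 treats follow-up endocrine laboratory tests as recommended only.
- **Access.** Under section 5.6, patients living elsewhere "will be allowed to obtain follow up care at home and forward records to the study team at the treating institution". The same section adds: "Once participants have reached 5 years post treatment, they may be compensated for a one time return visit to MGH if grant funding is available".

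The plan does not state whether event-free children are censored at their last audiogram or at their last contact. Nor does it say how a loss found after a gap in testing is dated.

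**The concern.** SNHL and endocrine deficits do not announce a date; they are found at a test. An ordinary actuarial estimate treats the detection date as the event date. Take a child who has no audiogram in years 1 to 3 and is tested at year 4 or 5. That child has not died, progressed, dropped out or been lost, so none of the stated censoring rules applies. The child sits in every risk set up to year 3 as event-free, and a loss that arose in year 2 enters the curve at year 4 or 5. Censoring at the last audiogram does not cure this, because this child's last audiogram is the late one.

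The 3-year rate decides whether protons are declared better, and under attendance unrelated to hearing the error runs towards declaring improvement. The evaluable numbers leave no room for missed tests: 60 × 0.80 = 48 and 30 × 2/3 = 20 allow only for progression or death.

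**Working it through.** **1. The plan's own figures (exact binomial).**
- Standard risk: P(X ≤ 14 | 48, 0.40) = 0.081 and P(X ≤ 14 | 48, 0.25) = 0.800. The plan states 8% and 80%.
- High risk: P(X ≤ 7 | 20, 0.50) = 0.132 and P(X ≤ 7 | 20, 0.30) = 0.772. The plan states 13% and 77%.

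All four reproduce, but only if every child's status at 3 years is known.

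**2. A hand calculation.** Let m be the share of children with no audiogram between baseline and year 5, all tested at year 5, with events dated then. The 3-year estimate is (1 − m) × true rate. The value of m is assumed.

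| m | Standard risk, true 40% | P(≤ 14 of 48) | High risk, true 50% | P(≤ 7 of 20) |
|---|---|---|---|---|
| 0 | 40% | 0.08 | 50% | 0.13 |
| 10% | 36% | 0.20 | 45% | 0.25 |
| 20% | 32% | 0.40 | 40% | 0.42 |
| 30% | 28% | 0.64 | 35% | 0.60 |

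**3. Independent attendance, by simulation.** Assumptions, none of them in the documents except the 40% null: true SNHL 40% at 3 years and 45% at 5; permanent loss; constant hazard within years 0 to 3 and 3 to 5; audiograms on each anniversary; attendance independent of hearing; event-free children censored at their last audiogram, which is the rule kindest to the plan. The cut is 14/48 = 29.2%, applied to the actuarial 3-year estimate.

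| Attendance, years 1–4 / year 5 | 3-year estimate | False claim, all followed to year 5 | False claim, follow-up staggered over 3–8 years |
|---|---|---|---|
| 100% / 100% | 40% | 0.08 | – |
| 80% / 85% | 37% | 0.14 | 0.11 |
| 60% / 85% | 33% | 0.31 | 0.22 |
| 40% / 85% | 26% | 0.69 | 0.47 |

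The staggered column reflects section 14.2: five years of accrual and a 3-year minimum follow-up mean that not every child can reach year 5. For high risk at 60% / 85%, with all followed to year 5, a true 50% is estimated at about 41% and the false-claim chance goes from 0.13 to about 0.33.

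**4. Does the funded visit drive it?** The control is equal attendance in all five years (true rise 5 points).

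| Years 1–4 / year 5 | 3-year | 5-year | Rise (points) |
|---|---|---|---|
| 60% / 60% | 33.5% | 46.8% | 13.3 |
| 60% / 85% | 32.9% | 45.8% | 12.9 |
| 40% / 40% | 29.6% | 51.4% | 21.8 |
| 40% / 85% | 26.0% | 46.1% | 20.1 |

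Better year-5 attendance lowers the 3-year estimate (by 0.6 and 3.6 points). It does not enlarge the rise. The false-claim chance moves from about 0.26 to 0.31 at 60% earlier attendance, and from about 0.5 to 0.69 at 40%.

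**5. Children who never return.** With a true 50% / 55% and 20% never examined after baseline, censoring at the last audiogram gives 50% / 55%, so no bias. Censoring at a year-5 contact date gives 40% / 44%. The unstated censoring date therefore matters by itself.

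**6. The alternative.** A Turnbull (interval-censored) estimate on the data of step 3 (all followed to year 5) returns 40% and 45% at both 60% / 85% and 40% / 85%, with a false-claim chance of no more than about 0.10.

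**The case against.** The strongest reply is that the text never says that untested children are carried as event-free. Sections 14.1 and 14.4 censor drop-outs and losses, and step 5 shows that censoring at the last audiogram removes the bias for children who do not return. That is right for them. It does not reach the child who returns after a gap, and no rule in the plan does.

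The reply can also say that the sizes are pessimistic. Audiograms are recommended before each platinum cycle, extra audiograms are collected, home records are accepted, and adverse events are sought at each contact. If 75% of the 3-year losses arise in year 1 and follow-up is staggered, the 60% / 85% case falls to about 0.12. This stands as a limit on the magnitude. Attendance could also depend on hearing, and then the bias could go either way.

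A reader might infer from section 5.6 that the funded year-5 visit causes an artificial jump between 3 and 5 years. The documents do not support that. The visit is a single one, discretionary and dependent on funding; it is available from year 5 rather than at year 5; and section 5.6 does not require an audiogram at it. Step 4 shows the same or a larger rise with no gain in year-5 attendance. The rise comes from missed tests and late dating.

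**Conclusion.** The point holds as a conditional bias. Optional testing, a right-censored estimator and no stated dating or censoring rule together can push the 3-year SNHL rate down and raise the chance of a false claim of improvement. For standard risk, that chance is about 0.11 to 0.14 at 80% attendance in years 1 to 4, 0.22 to 0.31 at 60% and 0.47 to 0.69 at 40%, against a planned 0.08. Each range runs from staggered follow-up to everyone followed to year 5, with 85% attendance at year 5. The figures are lower if most losses occur early. They rest on attendance that is independent of hearing and that the documents do not report, so they show sensitivity and do not predict the bias in this trial. The same mechanism applies to endocrine deficits found by testing, though no decision rule hangs on those. The change should be made because the primary decision depends on the 3-year rate and the remedy is cheap.

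**What to change.** In section 14.4, for late complications found by testing (SNHL, endocrine):

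1. Replace the right-censored actuarial estimate with an interval-censored one (for example Turnbull). The event lies between the last assessment without it and the first with it. Event-free children are censored at their last assessment.
2. Read the estimate at 3 and 5 years, and apply the section 14.1 decision to the 3-year value (cuts of 14/48 = 29.2% and 7/20 = 35%).
3. Report the number assessed in each year.
4. State that the method assumes attendance unrelated to hearing status, and add a sensitivity analysis in which it is related.

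The cost is SAP wording and standard software. No new data or visits are needed, and the funded-visit provision can stay as it is. The price is a somewhat wider interval around the 3-year rate.

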6. EXPECTED TOXICITIES AND DOSING DELAYS/DOSE MODIFICATIONS

Toxicity assessments will be done using the CTEP Active Version NCI Common Terminology Criteria for Adverse Events (CTCAE) which is available at:

http://ctep.cancer.gov/protocolDevelopment/electronic_applications/ctc.htm.

If possible, symptoms should be managed symptomatically. In the case of toxicity, appropriate medical treatment should be used (including anti-emetics, anti-diarrheals, etc.).

All adverse events experienced by participants will be collected from the time of the first dose of study treatment, through the study and until the final study visit. Participants continuing to experience toxicity at the off study visit may be contacted for additional assessments until the toxicity has resolved or is deemed irreversible.

